Pre-diabetes and Type II diabetes involve an impaired post-receptor response to insulin that hinders the glucose uptake response after meal consumption.¹⁷⁻¹⁹ Chronic hyperglycemia and the resulting compensatory hyperinsulinemia promote a cohort of acute and chronic sequelae including cardiovascular disease, liver complications, central nervous system degeneration and hyperglycemic osmotic stress.²⁰⁻²³ Axulin is a natural health product consisting of a mixture of extracts from herbs and vegetables present in normal diets which was identified by screening more than 100,000 compounds and extracts in a patented cell-culture based assay system targeting the IRS proteins. In vitro, Axulin has marked effects on the IRS-2 branch of the insulin signaling cascade to enhance downstream insulin signaling. Axulin has been shown in animal models to increase glucose uptake in peripheral tissues and decrease circulating blood glucose and triglyceride concentrations. Regular supplementation of the diet with Axulin would be expected to reduce the incidence of associated pre-diabetic and diabetic complications, resulting in an increased quality of life for patients without resorting to current anti-diabetic prescription drugs such as metformin and others that may have substantial unwanted side effects in patients.

HYPOTHESES

Axulin will reduce postprandial glucose and insulin responses in a dose-dependent fashion in healthy subjects without diabetes. The reduction in glucose and insulin will be relatively greater in insulin-resistant than insulin-sensitive subjects.

OBJECTIVES

The primary objective of this study is to determine the dose of Axulin which will reduce the incremental area under the blood glucose response curve (AUC) elicited by 75g oral glucose in healthy subjects by $\geq 33\%$.

The secondary objectives are to determine the dose-response effects of Axulin on:

- blood glucose and serum insulin AUC
- % reduction of insulin AUC
- the blood glucose and serum insulin increments at 15, 30, 45, 60, 90 and 120min
- insulinogen index
- Matsuda insulin sensitivity index
- ISSI-2 index of beta-cell function
- incremental blood lipid response at 120min
- plasma triglyceride response
- plasma axulin response

The other objectives are to determine whether the effects of Axulin on glucose, insulin and triglyceride responses differ in lean vs overweight subjects and to determine whether the effects of Axulin on postprandial responses are similar when administered in capsule versus tablet form.

SUBJECTS

Inclusion criteria

Subjects will be males or non-pregnant, non-lactating females aged 18-60 years who have no history of diabetes and are in good health. Lean subjects will have a BMI >18.5 and $<25.0\text{kg}/\text{m}^2$, overweight subjects will have a BMI ≥ 25.0 and $<35.0\text{kg}/\text{m}^2$. Subjects taking stable doses (for at least 4 weeks of signing the consent form) of the birth control pill, thyroxin replacement therapy, statins, fibrates, cholesterol absorption inhibitors, anti-hypertensive medications, aspirin, non-steroidal anti-inflammatories and/or mild anxiolytics or sedatives can be included.

Female subjects of child-bearing potential must, for the duration of the study, be using one of the following birth control methods: total abstinence, a hormonal birth control method (oral, injectable, transdermal, or intra-vaginal), intrauterine device, or confirmed successful vasectomy of partner.

Exclusion criteria

- Fasting serum glucose $>6.9\text{mmol}/\text{L}$ (124mg/dL)
- HbA1c $>6.4\%$
- Fasting serum triglycerides $>4.5\text{ mmol}/\text{L}$ (399 mg/dL)
- Fasting LDL cholesterol $>4.99\text{ mmol}/\text{L}$ (192 mg/dL)
- Blood pressure >149 systolic or >89 diastolic
- Serum creatinine, or aspartate- or alanine transaminases >1.2 times upper limit of normal
- White cell count, red blood cell count, hemoglobin or hematocrit outside normal range
- Hospitalization for surgery or a medical condition within 3 months of signing the consent form

- Use of any drug to treat diabetes
- Use of medications other than those listed above or the presence of any condition which might, in the opinion of [name], either: 1) make participation dangerous to the subject or to others, or 2) affect the results
- Allergy or sensitivity to tarragon, chromium, escarole, lettuce, microcrystalline cellulose, inulin, food colouring (FD&C Yellow#5 and Blue#1) or vegetable-based capsules (silicon dioxide, titanium dioxide, hydroxypropylmethylcellulose)

Number of subjects

The primary endpoint is the % reduction in 2-hour incremental AUC for glucose. Using the t-distribution with 2-tailed $p<0.05$ and assuming an average CV of within-individual variation of 2-hour incremental AUC values of 25%, $n=20$ subjects (10 lean and 10 overweight) has 80% power to detect a 17% difference in AUC, 90% power to detect a difference of 19% and 99% power to detect a difference of 26%. Within each subject group ($n=10$) there is 80% power to detect a difference in AUC of 25%, and 80% power to detect a 33% difference between the responses of lean and overweight subjects. To allow for 10% dropout, we will recruit $n=11$ lean and $n=11$ overweight subjects.

Subject Recruitment

Participants will be recruited from the pool of participants at GI Laboratories who have indicated that they are willing to be contacted and asked if they wish to participate in new studies. If an insufficient number of subjects can be recruited, then a newspaper advertisement will be used to recruit new subjects.

Selection of participants

Participants willing to be considered will be invited to come to the research centre to have the study procedures explained to them and be given a copy of the consent form which they may either sign then, take away to sign at a later date, or decline to participate. Participants will be encouraged to ask any questions they may have and not to sign the consent form until all of their questions have been answered to their satisfaction. Those who consent to participate will come to the research centre for a pre-selection visit when subject eligibility will be determined. During this visit, the 10-14hr overnight fasted participants will complete a questionnaire (Appendix 1) to assess medical history, and lifestyle factors, have height, weight, waist circumference and blood pressure measured, and have a blood sample drawn for measurement of glucose, HbA1c, lipids, creatinine, AST, ALT and complete blood count. Females will have a pregnancy test.

PROCEDURES

The study will have a randomized block design with repeated measures. One block, which will be double-blinded, will test the effect of Axulin capsules; the other block, which will be open label, will test the effect of Axulin tablets. Within each participant, the order of the blocks will be randomized and within each block the order of the treatments will be randomized.

Eligible participants will be instructed to maintain stable dietary and exercise habits and for the duration of the study, to avoid vigorous physical activity for 24hr before each visit and to and consume their normal dinner the night before each visit. At each visit current use of medications and natural health products participants will be reviewed with each participant and any changes will be discussed with the investigator. Female participants will be advised that if they become pregnant during the study they are to contact the investigators and discontinue their participation immediately.

Each subject will be studied on 6 separate days with at least a 3-day interval between tests. On each test day, subjects will come to GI Labs ([name]) in the morning after a 10-14h overnight fast. On each test occasion the subject will be weighed, and give fasting finger-prick and venous blood samples. Blood from a forearm vein will be collected into a 6ml EDTA tube (Vacutainer, BD Canada, Mississauga, ON). Finger-prick blood samples will be collected into 2 separate vials: one (2-3 drops blood into a fluoro-oxalate tube) for glucose analysis and the other (6-8 drops of blood into an 0.3ml Microvette with clot activator, Sarsted, Germany) for insulin. After the fasting sample the subject will take 12 capsules or 2 tablets with a drink of 250ml water. Subjects will rest for 3-10min and have their blood pressure measured; 40min after swallowing the first capsule or tablet a finger-prick blood sample (2-3 drops for glucose and 6-8 drops for insulin analysis) will be collected and then subjects will consume 82.5g dextrose (containing 75g anhydrous glucose) dissolved in 300ml water within 5min plus a drink of 150ml water within 10min of starting the glucose drink. Further finger-prick blood samples for glucose (2-3 drops) and insulin (6-8 drops) will be obtained at 15, 30, 45, 60, 90 and 120 min after starting to drink the glucose solution. Venous blood samples (7ml) will be collected after the 60 and 120 min finger-prick. During the test subjects will remain seated quietly except for trips to the washroom if necessary. After the last blood sample subjects will be offered a snack and be free to leave.

Treatments

The 6 treatments administered will consist of the following:

- 12 placebo capsules with 250ml water (0g Axulin)
- 250ml water alone (0g Axulin)

- 4 placebo and 8 Axulin capsules (2g Axulin)
- 16 Axulin capsules (4g Axulin)
- 2 Axulin tablets (2g Axulin)
- 4 Axulin tablets (4g Axulin)

Each placebo capsule contains 250mg inulin, each identical-looking Axulin capsule contains 250mg Axulin. It is anticipated that Axulin will be sold in tablets because 1g can be compacted into a tablet without loss of biological activity, but, because Axulin is a low-density powder, only 400mg can be placed in a capsule of similar size. We will use capsules in this study because it is more economical to produce the relatively small number of identical-looking placebo capsules required as compared to producing placebo tablets. To obtain doses in 1g increments, we will use smaller capsules containing 250mg each. The rationale for including tablets in the study is that Axulin in tablet form might be more slowly bioavailable than when encapsulated; thus, it is

important to determine whether the effects of Axulin tablets on postprandial responses is similar to the same dose taken in capsules.

Blinding

The number of Placebo and Active Axulin capsules and tablets required for the study will be provided to GI Labs. A person not involved in any other aspect of the study will make up 6 small zip-lock plastic bags for each subject labelled with a subject number and visit number and containing the treatment for visits 1 through 6 (the bag for the water alone treatment will be empty). The treatments will be randomized as shown in Table 1. The order of the blocks and the order of the treatments within each block were randomized using the @rand() function of Excel with 2 blocks of 6 created for lean subjects and 2 blocks for overweight subjects; the 2 extra orders are for use in case of drop-outs so that at least n=20 subjects complete the study (see Table 1). The person labeling and filling the bags with the treatments will assign the treatments to the codes and place the treatment assignments in a sealed opaque envelope kept in an accessible location. The envelope will be opened only after the study has been completed and the database locked, or in case of emergency if required for participant safety.

Table 1: Randomization Scheme

ID	Group	Visit 1	Visit 2	Visit 3	Visit 4	Visit 5	Visit 6
1	Lean	A	B	C	E	D	F
2	Lean	B	C	A	E	F	D
3	Lean	F	D	E	C	A	B
4	Lean	B	A	C	F	E	D
5	Lean	D	E	F	A	C	B
6	Lean	D	F	E	C	B	A
7	Lean	F	D	E	A	C	B
8	Lean	C	B	A	D	E	F
9	Lean	D	F	E	B	C	A
10	Lean	C	A	B	E	D	F
11	Lean	B	A	C	E	F	D
12	Lean	F	E	D	A	B	C
21	Overweight	D	E	F	C	B	A
22	Overweight	F	D	E	B	A	C
23	Overweight	A	B	C	E	D	F
24	Overweight	A	C	B	F	E	D
25	Overweight	B	C	A	E	F	D
26	Overweight	C	A	B	D	F	E

27	Overweight	B	C	A	F	D	E
28	Overweight	D	F	E	B	A	C
29	Overweight	D	E	F	C	B	A
30	Overweight	F	E	D	A	B	C
31	Overweight	A	C	B	E	F	D
32	Overweight	E	D	F	C	A	B

Instructions: please assign capsules to codes A, B or C, and tablets or empty bag to codes D, E or F. Place treatment assignments into a sealed opaque envelope and keep the envelope in an accessible location. Treatments are as follows:

BLOCK 1 (A, B or C)

- Placebo 1; 16 Placebo capsules
- 2g Axulin caps: 4 Placebo capsules plus 8 Axulin capsules
- 4g Axulin caps: 16 Axulin capsules

BLOCK 2 (D, E or F)

- empty bag
- 2g Axulin tablets: 2 Axulin tablets
- 4g Axulin tablets: 4 Axulin tablets

Biochemical Analysis

Finger-prick blood samples for glucose analysis will be placed in the refrigerator immediately after being obtained and at the end of the test placed in a -20°C freezer until analysis which will be performed within 5 days. Glucose analysis is done using an YSI model 2300 STAT analyzer (Yellow Springs, OH). The microvette tubes used to collect blood for insulin analysis will be centrifuged at 3622×g for 2 min and the serum transferred to labeled polypropylene tubes and stored at -20°C prior to analysis of insulin using the Human Insulin EIA Kit (Alpco Diagnostics). Venous blood samples will be stored at 4°C until the end of the study after which they will be centrifuged at ~1400×g for 10 min and the plasma removed and separated into 2×1ml aliquots; 1 for analysis of triglycerides at St. Michael's Hospital biochemistry laboratory and the other for measurement of the active ingredient in Axulin by liquid chromatography/mass spectrometry.

Statistical Analysis

Incremental areas under the blood glucose, insulin and triglyceride response curves (AUC), ignoring area below fasting, will be calculated. Blood glucose and insulin concentrations and AUC values will be analyzed using repeated measures ANOVA examining for the main effects of dose, form (tablets vs capsules) and subject group (lean vs overweight) and their interactions. After demonstration of significant heterogeneity, differences between individual means will be assessed using Tukey's test to adjust for multiple comparisons.

Informed Consent

The GI Testing protocol has been approved by the Western Institutional Review Board® which meets all requirements of the US Food and Drug Administration (FDA), the Department of Health and Human Services (DHHS), the Canadian Health Protection Branch (HPB), Canadian

Institutes for Health Research (CIHR) and the European Community Guidelines. Informed consent is obtained from all subjects for each series of tests they participate in.

Participant Withdrawal Criteria

The Investigator may elect to withdraw the participant from the study or the participant may withdraw from the study at any time. Reasons for withdrawing include, but are not limited to:

- Development of an exclusion criterion during the course of the study
- Study product never consumed
- Participant was lost to follow-up
- Participant did not follow study procedures
- Participant elected to withdraw from the study for any reason
- Investigator elected to remove participant from the study for any reason
- Subject takes longer than the specified time to complete the study

In the case of premature withdrawal, all planned assessments for the end of the study visit will be completed and the sponsor will be informed as soon as possible. The subject's Case Report Form ("CRF") will be completed including the final assessment. The date and main reason for the premature withdrawal will be clearly documented in the subject's file and written down on the CRF

ADVERSE EVENT REPORTING

An adverse event (AE) is any symptom, injury, illness, or medical/surgical procedure whether planned or not or whether associated with the study foods or not. AEs will be assessed at each visit and recorded in the Case Report Forms. AEs will be evaluated for duration, severity, seriousness, and causal relationship to the food items provided in the study by the study physician who will decide if any action is required and provide referral, treatment, and/or follow-up as appropriate until resolved, judged to no longer be clinically significant, or if a chronic condition, until fully characterized. Research staff will record the final outcome and resolution date of the event wherever possible. The action taken and the outcome will be recorded in the Case Report Form.

It is anticipated that participants enrolled in the study will be clinically managed without the need to add medications or to change the dosage(s) assigned to their current medications. In the event that additional medication is required, or an increase in their medication dosage is warranted, these changes will be recorded as adverse events.

Investigators are required to report adverse events that fit the following criteria within 10 working days of the time the investigator becomes aware of them:

- Event is **Unexpected** (in terms of nature, severity, or frequency) given (a) the research procedures that are described in the protocol-related documents, such as the IRB-approved research protocol and informed consent document, or the

Investigator Brochure; and (b) the characteristics of the subject population being studied.

- **Related or possibly related** to participation in the research (possibly related means there is a reasonable possibility that the incident, experience, or outcome may have been caused by the procedures involved in the research); and
- Suggests that the research **places subjects or others at a greater risk of harm** (including physical, psychological, economic, or social harm) than was previously known or recognized.

If the adverse event is clearly not related to the study drug, device, procedures, or washout process, it would not represent a risk to other subjects in the research or a “problem” for the study and, therefore, does not have to be reported to WIRB.

The Principal Investigator, [name], will be informed within 48 hrs of the nature of the reportable AE and the treatment allocation of the participant in whom it occurred by sending a copy of the AE report via email ([contact]). [name] will track all reportable AEs and notify the sponsors if they occur.

In addition to the above, all adverse events will be reported to Health Canada. All serious adverse events (any adverse event that results in death, is life-threatening, requires in-patient hospitalization or prolongation of existing hospitalization, results in persistent or significant disability/incapacity or is a congenital anomaly/birth defect) will be reported to Health Canada, the Sponsor and the IRB within 24hr of their ascertainment.

Risks

Healthy volunteers have been found to be able to tolerate doses of up to 60g of resistant maltodextrins with few symptoms (Storey et al. 2007). Since the test meals used in this study contain a maximum of 12g resistant starch, we do not expect subjects to experience any GI symptoms, or if symptoms do occur, they would be very mild (eg. mild flatulence). However, there may be rare occurrences of study product intolerance, as manifested by severe gastrointestinal symptoms (such as crampy gas or watery stools), eczema, rashes, or other signs of allergy, or infection.

Dispensing

It is the responsibility of the Investigator or his designee to ensure that study product is only provided to study participants.

All study products will be consumed during test sessions at Glycemic Index Laboratories and will not be dispensed to subjects to consume outside of the facility. The specific serving size for each product will be provided to the Investigator along with instructions for administration of each product.

Source documents and archiving

All documents relating to the study will be kept by the investigator: the original informed consent form, source documents, copy of the CRF, copy of the accountability of products

administered, copy of the WIRB (ethics committee) approval and correspondence with the sponsor. The investigator will authorize direct access to the source documents during monitoring. As required by Canadian law, documents will be kept by the investigator for at least 25 years after the closure of the study.

BUDGET

Expense Category	Amount (\$CDN)
Screening	8,450
Hospital Lab fees	3,475
WIRB submission	4,375
Subject payments	9,840
Supplies	14,370
Staff	
Study coordinators: 144hr @ \$45	6,480
Junior Staff: 138hr @ \$30	4,140
Lab technicians: 439hr @ \$30	13,170
Data analysis	4,000
Protocol/Report /Manuscript	5,800
Space utilization	31,400
TOTAL	105,500

References

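### The insulin-resistance hypothesis is tested only through BMI group, in an ANOVA on AUC with no relative scale stated, so equal percentage reductions can look like a group difference

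*Combined protocol and SAP*

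**What the plan says.** **Hypotheses.** The second hypothesis is "The reduction in glucose and insulin will be relatively greater in insulin-resistant than insulin-sensitive subjects". It names insulin resistance as the modifier and describes the difference as a relative one.

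**Objectives.** The matching item stands among the other objectives, after the primary and secondary ones. It asks whether effects on "glucose, insulin and triglyceride responses differ in lean vs overweight subjects". The modifier is now body size.

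**Inclusion criteria.** The groups are defined by BMI alone: "Lean subjects will have a BMI >18.5" and below 25.0, and "overweight subjects will have a BMI ≥ 25.0" and below 35.0. No section defines insulin resistance, gives a cut-off for it, or says that BMI stands in for it.

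**Number of subjects.** The primary endpoint is percent reduction in 2-hour incremental glucose AUC. With 10 per group the plan claims "80% power to detect a 33% difference between the responses of lean and overweight subjects".

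**Statistical Analysis.** The outcome and method are given as "Blood glucose and insulin concentrations and AUC values will be analyzed using repeated measures ANOVA". No log transform, ratio or percent change is mentioned. The model terms are set out next, with the analysis "examining for the main effects of dose, form (tablets vs capsules) and subject group (lean vs overweight) and their interactions".

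**Procedures.** On each of six test days, subjects "give fasting finger-prick and venous blood samples". The finger-prick sample includes a vial for insulin and is taken before the product is swallowed. The Matsuda and ISSI-2 indices appear only as dose-response outcomes, not as modifiers.

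**The concern.** Two things separate the hypothesis from its test.

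The first is scale. An interaction on untransformed AUC asks whether the absolute drop differs between groups. A group with a larger control AUC has a larger absolute drop even when the percentage drop is the same. If overweight subjects have larger responses, the test can appear to confirm a relative claim that is false. The mismatch can also work the other way and hide a real relative difference.

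The second is the modifier. BMI group is an indirect marker of insulin resistance. Any participant whose insulin status does not match the BMI group dilutes the contrast. Fasting insulin, a marker nearer to the hypothesis, is measured at every visit but is given no role as a modifier.

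At stake is the interpretation of one stated hypothesis. The primary dose-finding objective is not affected by this point.

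**Working it through.** **1. The plan's own figure.** Inputs from Number of subjects: 10 per group, two-sided 0.05, t-distribution, 25% variability, 33% difference. A two-sample noncentral t with SD 0.25 for the subject-level percent difference has noncentrality 0.33 / (0.25 × √(2/10)) = 2.95 on 18 df. Power is 79.7%, so the stated 80% reproduces. Using 0.25 × √2 = 0.354 as the SD of a difference between two visits gives 50.6%, so the plan took 25% as the SD of the difference. The statement is in percent terms and concerns the BMI contrast.

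**2. What the raw interaction measures.** Set lean control AUC to 1 and overweight control AUC to R, with the same 33% reduction in both groups. The absolute reductions are 0.33 and 0.33R, so the raw interaction is 0.33 × (R − 1).

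| R | Raw interaction | Relative difference |
|---|---|---|
| 1 | 0 | 0 |
| 1.25 | 0.0825 | 0 |
| 1.5 | 0.165 | 0 |
| 2 | 0.33 | 0 |

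The converse also occurs. With R = 1.5, a 30% reduction in lean and 20% in overweight gives absolute drops of 0.30 and 1.5 × 0.20 = 0.30. The raw interaction is then zero although the relative effects differ.

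**3. How often the raw test rejects when relative effects are equal.** From the plan: 10 per group, within-person CV 25%, 33% target reduction. Assumed: between-person CV 30%, R from 1 to 2, log-normal AUC, the same effect at every active visit. The log-scale SDs are √ln(1 + 0.25²) = 0.246 within and √ln(1 + 0.30²) = 0.294 between. The outcome is control minus active AUC per subject (raw), or the difference in log AUC, compared between groups by t-test at two-sided 0.05. The six visits comprise two zero-dose treatments (placebo capsules, water alone) and four active ones.

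| R | Raw, 1 control + 1 active | Raw, 2 control + 4 active | Log ratio, either |
|---|---|---|---|
| 1 | 5% | 5% | 5% |
| 1.25 | 7% | 10% | 5% |
| 1.5 | 13% | 22% | 5% |
| 2 | 26% | 51% | 5% |

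These are simulation results; repeat runs differ by about one percentage point. A test on each subject's percent reduction also stays at about 5%. Using more visits worsens the raw test, because better precision makes the spurious interaction easier to detect.

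**4. What a fasting-insulin moderator could add.** Assumed: true moderation of 0.20 log units per SD of insulin resistance, n = 20, within-person CV 25%, one control and one active visit. The documents give no correlation of either marker with insulin resistance, so both are shown as ranges.

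| Modifier | Correlation with insulin resistance | Power |
|---|---|---|
| BMI group (10 vs 10) | 0.3 / 0.5 / 0.7 | 8% / 14% / 23% |
| Continuous fasting insulin | 0.5 / 0.7 / 0.95 | 18% / 33% / 59% |

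At equal correlation the gain is modest: 18% against 14% at 0.5, and 33% against 23% at 0.7. With two control and four active visits, BMI-group power rises to about 11%, 22% and 42%.

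**The case against.** The strongest reply is that the plan does address the hypothesis. Objectives restates it as lean versus overweight, recruitment is balanced on that factor, the interaction is in the model, and the detectable difference of 33% is disclosed. That stands. A reader might infer that the hypothesis goes untested; the documents show instead that it is tested by proxy, among the other objectives.

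The untransformed scale is also an inference from silence. The primary endpoint and the between-group power statement are in percent, and percent reduction of insulin AUC is a secondary objective. The authors may have intended a relative analysis, but Statistical Analysis names AUC values and does not connect the model to the percent endpoint. The word *relatively* could mean no more than *comparatively*, though the percent endpoint favours the ratio reading.

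A reader might further infer that fasting insulin would far outperform BMI group. That requires a correlation with insulin resistance near 0.95. Averaging six values improves the reliability of mean fasting insulin, not its validity as a marker of insulin resistance, and the documents give no figure for validity.

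The moderator has two further limits. Only the visit 1 value precedes all product exposure, since later visits may follow a dose by as little as 3 days. For the insulin outcome, fasting insulin is also the baseline from which the incremental area is calculated.

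**Conclusion.** The concern holds as a mismatch of scale and of modifier. Read as written, the dose-by-group interaction tests absolute reduction, while the hypothesis and the primary endpoint are relative. With equal 33% reductions in both groups, false rejection is about 7% to 26% with one control and one active visit, and about 10% to 51% with two and four, for AUC ratios of 1.25 to 2. These figures rest on an assumed between-person CV of 30% and on AUC ratios that the documents do not give. If the groups have equal control AUC there is no inflation.

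The BMI substitution is a real but lesser gap. It means that a lean/overweight result should not be reported as a finding about insulin resistance. The documents do not support a claim that the hypothesis is untested, or that a fasting-insulin analysis would be well powered at n = 20.

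**What to change.** In Statistical Analysis, before unblinding:

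1. State that the dose-by-group interaction is tested on log AUC, or on each participant's percent reduction, consistent with the primary endpoint. Give a rule for zero incremental areas, which have no logarithm.
2. Keep lean versus overweight as the group objective, and say that it is a BMI proxy for insulin resistance.
3. Prespecify one analysis, labelled exploratory at n = 20, of dose by continuous log fasting insulin on the same relative scale. Use each participant's mean pre-dose fasting value over the visits, with visit 1 alone as a sensitivity analysis. Exclude the 40-minute sample, which follows dosing. Note that for the insulin outcome the fasting value also enters the incremental AUC.

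The cost is a few sentences and one additional model. No new samples, visits or participants are needed. If the moderator analysis is added after unblinding, it would have to be reported as post hoc.

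### The stated detectable differences need a contrast SD of 25%; if 25% is the CV of one AUC, as worded, they fit only a dose contrast averaged over capsules and tablets and are too favourable for one treatment against another

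*Combined protocol and SAP*

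**What the plan says.** The power statement under Number of subjects uses a two-sided 5% t-test, "assuming an average CV of within-individual variation of 2-hour incremental AUC values of 25" (per cent). With 20 subjects it "has 80% power to detect a 17% difference in AUC, 90% power to detect a difference of 19" (per cent), and a third figure gives 99% power at 26%. Within a group of 10, "there is 80% power to detect a difference in AUC of 25" (per cent). The last figure is "80% power to detect a 33% difference between the responses of lean and overweight subjects". The paragraph does not say which treatments are compared or whether AUCs are averaged before comparison.

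The design is set out under PROCEDURES and Treatments. "Each subject will be studied on 6 separate days", one for each of six treatments: 0, 2 and 4 g in a capsule block and 0, 2 and 4 g in a tablet block. "One block, which will be double-blinded, will test the effect of Axulin capsules"; the tablet block is open label, and its zero-dose arm is "250ml water alone (0g Axulin"). Treatments also calls it "important to determine whether the effects of Axulin tablets on postprandial responses is similar to the same dose taken in capsules". Statistical Analysis plans a repeated-measures ANOVA with dose, form and subject group, followed by Tukey's test on individual means, without saying which means form the family.

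**The concern.** A CV of AUC values describes one AUC. A difference between two single AUCs from the same subject is more variable than either, by a factor of up to √2. The power statement appears to use 25% directly as the SD of the difference. That is legitimate for some contrasts in this design and not for others, and the paragraph does not distinguish them.

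At stake is how non-significant results will be read. The comparison of Axulin capsules with placebo capsules is the only blinded one, and the comparison of tablet with capsule at the same dose is a named aim. Both set one test against one test. A reader relying on the paragraph could treat a null result there, or within a group of 10, as having had 80% power against 17% or 25% when the power was nearer 50-60%.

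**Working it through.** **Inputs.** From Number of subjects: two-sided alpha 0.05, t-distribution, 25%, n=20 (10 lean and 10 overweight). From PROCEDURES and Treatments: one test per treatment per subject, three dose levels in each of two forms. Assumptions: independent errors with equal SD or equal CV across visits, no variation between subjects in the response to treatment, and differences expressed as a percentage of the control mean.

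**Reproducing the stated figures.** Detectable difference = (t at 0.975 + t at the power) × SD/√n, with contrast SD 25%:
- n=20, 19 df, 80%: (2.093 + 0.861) × 25/√20 = 16.5 (stated 17)
- 90%: (2.093 + 1.328) × 5.590 = 19.1 (stated 19)
- 99%: (2.093 + 2.539) × 5.590 = 25.9 (stated 26; the exact noncentral t gives 25.3)
- n=10, 9 df, 80%: (2.262 + 0.883) × 25/√10 = 24.9 (stated 25)
- 10 vs 10, 18 df, 80%: (2.101 + 0.862) × 25 × √(2/10) = 33.1 (stated 33)

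All five are recovered after rounding. An SD of 25√2, an unpaired 20 vs 20 comparison, a log-scale SD and a normal approximation do not recover them.

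**When the contrast SD is 25%.** With m tests per arm and a 25% CV for one AUC, the SD of the within-subject difference is 25√(2/m) if the SD is constant. If the CV is constant it is 25√((1 + (1−d)²)/m), with d the reduction as a fraction. At constant SD, m=2 gives exactly 25. This is a dose contrast averaged over capsules and tablets, whose 0 g level pools placebo capsules with open-label water alone.

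**One treatment against another (m=1), unadjusted.** At constant SD the contrast SD is 25√2 = 35.4. Then n=20 needs 2.954 × 35.36/√20 = 23.4% for 80% power. At constant CV the equation is solved for d: at d = 21.0% the SD is 25√(1 + 0.79²) = 31.9, and 2.954 × 31.9/√20 = 21.0%. The other entries follow in the same way.

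| Comparison | Stated | Constant CV | Constant SD |
|---|---|---|---|
| n=20, 80% power | 17% | 21.0% | 23.4% |
| n=20, 90% power | 19% | 24.0% | 27.0% |
| n=10, 80% power | 25% | 30.3% | 35.2% |
| Power at 17%, n=20 | 80% | 60% | 53% |
| Power at 25%, n=10 | 80% | 62% | 51% |
| Power at 33%, n=20 | – | 99.6% | 98% |
| Power at 33%, n=10 | – | 87% | 75% |

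Lean vs overweight for a single treatment, constant SD: 33.1 × √2 = 46.8%, and power at 33% is 51%. Both this figure and the form-averaged 33.1% leave out between-subject variation in response.

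**Form main effect (m=3).** At constant SD the contrast SD is 25√(2/3) = 20.4, with 80% power at 13.5% (12.7% at constant CV). At 0 g, however, this effect compares placebo capsules with water alone. If forms differ only at 2 g and 4 g, the main effect is two-thirds of that difference, so 12.7-13.5% corresponds to 12.7 × 1.5 = 19% to 13.5 × 1.5 = 20% at the active doses.

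**With Tukey.** The family is not stated; three means with 36 df are assumed (critical t 2.444). The form-averaged dose contrast at n=20 then needs 17.0-18.5% for 80% power. A single capsule comparison needs 23.3-26.1%, and its power at 33% is about 95-99%.

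**The case against.** The strongest reply is that nothing has been miscalculated. All five figures reproduce, and the dose main effect in Statistical Analysis is the form-averaged contrast for which they hold. At constant CV they are even conservative for it (15.3% against 17% at n=20). If 25% was meant as the SD of a paired difference, they also hold, unadjusted, for single pairs. The reference to individual means may concern three dose means rather than six treatment means. All of this stands, so a reader who infers an arithmetic error, or that every figure is wrong, goes further than the documents allow.

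It does not remove the point. The assumption as worded is about AUC values, the figures carry no restriction to a form-averaged contrast, and that contrast is not the blinded comparison.

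A second reply is that the unadjusted paired-t figures are not the planned test. That is fair, but the stated figures are unadjusted too, and Tukey moves the single-treatment values further from them. A third is that the lean vs overweight figure could refer to AUC itself rather than to the response to Axulin. In that case a within-individual CV would not be the relevant variability, so this reading does not rescue the figure.

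**Conclusion.** The power statement is wrong as written for single-treatment comparisons, because its assumption and its figures agree only for a contrast that it does not name. With 25% as the CV of one AUC, the unadjusted figures stand for dose averaged over forms. For one treatment against another at n=20, 80% power needs 21.0-23.4% and 90% needs 24.0-27.0%. Within a group of 10, 80% power needs 30.3-35.2%. Lean vs overweight for a single treatment needs about 47% at constant SD.

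Two further inferences should be avoided. One is that the trial is too small: at the 33% reduction in the primary objective, a single treatment with 20 subjects has about 98-99.6% power unadjusted and about 95-99% with Tukey over three means, so n is not in question. The other is that the form main effect escapes the problem: its 0 g level compares no Axulin form, so its apparent 12.7-13.5% is about 19-20% at the active doses if that is where forms differ.

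The ranges run from constant CV to constant SD and rest on independent errors and no variation in response between subjects. The Tukey family and its degrees of freedom are assumptions.

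**What to change.** Keep n and reword the paragraph under Number of subjects:

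- Say whether 25% is the CV of one AUC or the SD of a within-subject difference. If it is the latter, correct the wording of the assumption; the unadjusted figures can then stay.
- If it is the CV of one AUC, limit the existing figures to the dose contrast averaged over capsules and tablets, and say that its 0 g level pools placebo capsules with water alone.
- In that case add single-treatment figures: n=20, 80% power at about 21-23% and 90% at about 24-27%; n=10, 80% power at about 30-35%; lean vs overweight about 47% at constant SD, with no between-subject variation in response. Quote one end of each range once the scale is fixed.
- Note that these are unadjusted and that the planned Tukey test makes them larger, for example 23.3-26.1% at n=20 if the family is the three capsule means.

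The cost is one rewritten paragraph and less favourable stated figures for single-treatment and subgroup comparisons. No subjects, visits or analyses are added.
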